9.11 Ethical Issues

Rationale for Subject Selection: Subject accrual for the study is available to both genders, racial and ethnic groups. No groups are being excluded from participation in the trial. Some of the subjects could become cognitively impaired as a consequence of, for example, their brain tumor. Patients who are 18 years old or older will be offered the opportunity to assign DPA prior to study entry. Adults who are cognitively impaired prior to study entry and who have not previously assigned DPA to a family member or friend will not be eligible for the trial, because they cannot give informed consent.

9.12 Participation of Children

Patients <21 years of age will be entered on this protocol. The primary objective of this trial is to determine if there is evidence of responses for patients receiving Pegylated interferon. The interferons have been extensively studied in both adults and children, and the side effects are well-described. Although pegylated interferon alpha-2b has not been extensively studied in children, we will use doses of interferon alpha-2b previously utilized in clinical trials, therefore we expect to see similar toxicity and similar side effects. The trial will be conducted by pediatric oncologists who have extensive experience in performing investigational drug trials in children. Patients will be cared for in the Aflac Cancer and Blood Disorder Center.

9.13 Risks and Benefits

Patients eligible for this trial are less than 21 years old. The primary risk to patients participating in this research study is from toxicity of pegylated interferon alfa-2b. The protocol provides for detailed and careful monitoring of all patients to assess for toxicity. Patients will be treated with therapeutic intent and response to the therapy will be closely monitored. Patients will also be at risk from the MRI contrast agent, Gd-DTPA (gadolinium). The risks of Gd-DTPA are well-defined and consist primarily of nausea. Allergic reactions are rare. The potential benefits from pegylated interferon alpha-2b are disease stabilization or shrinkage, a reduction in symptoms caused by the tumor/cancer, and prolonged survival and the potential to avoid and/or delay radiation. Therefore, this protocol involves greater than minimal risk to children, but presents the potential for direct benefit to individual subjects.

10.0 EVALUATION CRITERIA

10.1 Common Terminology Criteria for Adverse Events (CTCAE)

This study will utilize version 5.0 of the CTCAE of the National Cancer Institute (NCI) for toxicity and performance reporting. A copy of the CTCAE version 5.0 can be downloaded from the CTEP website

https://ctep.cancer.gov/protocoldevelopment/electronic_applications/docs/CTCAE_v5_Quick_Reference_5x7.pdf

Please note: 'CTCAE v5.0' is understood to represent the most current version of CTCAE v5.0 as referenced on the CTEP website

10.2 Methodology to Determine Tumor Measurement

All axial images should be obtained in a plane parallel to a line intersecting the bottom of the genu and of the splenium of the corpus callosum (modified AC-PC line) - to assure consistency of imaging plane. Coronal images should be obtained perpendicular to the axial images.

- 1) DAX TI, whole brain, 12 directions.
 - 2) Sagittal T1 weighted MP_RAGE (TR/TI 2300/900)
 - 3) Ax T2 weighted (TR ~4500, TE ~75)
 - 4) 3D Coronal FLAIR (TR/TI 4800/1650)
 - 5) Coronal 2D, fat saturated TSE through the orbits and chiasm (TR ~3,500, Te ~80)
 - 6) Axial 2d, fat saturated TSE through the orbits and chiasm (TR ~3,500, Te ~80)
- Post-Contrast
- 7) Axial, whole brain SPGR (TR/TE ~)
 - 8) Coronal 2d, fat saturated TSE through the orbits and chiasm (TR ~3,500, Te ~80)
 - 9) Axial 2d, fat saturated TSE through the orbits and chiasm (TR ~3,500, Te ~80)

Series 5 and 8 should have the same slice locations.

Series 6 and 9 should have the same slice locations.

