1.2 SECONDARY STUDY OBJECTIVES

1.2.1

To estimate event free survival (EFS) (based on standard two or three-dimensional tumor measurements) for children with recurrent, refractory or progressive Juvenile Pilocytic Astrocytomas and Optic Pathway Gliomas who are treated with Peginterferon.

1.2.2

To define the toxicities of long term weekly pegylated interferon alpha-2b in pediatric patients with refractory, recurrent and progressive Juvenile Pilocytic Astrocytomas and Optic Pathway Gliomas.

1.2.3

To compare response categories and EFS across the 3 MR sequences (T2-weighted, FLAIR, T1-weighted post-contrast).

1.2.4

To evaluate the quality of life for patients with recurrent, refractory and progressive Juvenile Pilocytic Astrocytomas and Optic Pathway Gliomas who receive therapy with pegylated interferon alpha-2b

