2.8 Imaging

Imaging of the tumor will be assessed with MRI of brain and /or spine with and without contrast performed on a 1.5 or 3T scanner. Progressive disease will be defined on the basis of a comparison of the baseline scan to the scan demonstrating best response. All axial images should be obtained in a plane parallel to a line intersecting the bottom of the genu and of the splenium of the corpus callosum to assure consistency of imaging plane. Coronal images should be obtained in a plane perpendicular to the axial images.

- 1) Axial diffusion tensor imaging whole brain
- 2) Sagittal, volumetric T1-weighted, gradient echo whole head
- 3) Axial T2-weighted fast spin echo (FSE) whole head
- 4) 3D Coronal FLAIR.
- 5) Coronal T2-weighted fast spin echo (FSE), fat saturated through the orbits and chiasm.
- 6) Axial T2-weighted fast spin echo (FSE), fat saturated through the orbits and chiasm.
- 7) Axial volumetric T1-weighted gradient echo post contrast whole brain.
- 8) Axial Oblique T1-weighted Fat Suppressed gradient echo post contrast, optic nerves and chiasm.
- 9) Coronal T1-weighted Fat suppressed gradient echo post contrast, optic nerves and chiasm. If imaging of the spine is needed, axial and sagittal T2 and post contrast T1 weighted images will be acquired. Diffusion images of the spine will be obtained if clinically indicated. Volumetric studies for MRI of the brain will be obtain to better evaluate the cystic component of the Low grade gliomas and be able to evaluate responses to the therapy. These sequences are the minimum required to evaluate the response to the treatment. Additional sequences such as MR spectroscopy can be obtained if clinically indicated per institutional protocols.

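### Sections 2.8 and 10.2 contradict each other on the dedicated post-contrast orbit/chiasm series: T1-weighted and fat-suppressed in 2.8, T2-type settings in 10.2

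*Combined protocol and SAP*

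**What the plan says.** Section 2.8 (Imaging) lists nine MRI series and describes them as the least needed to evaluate response. Series 5 is "Coronal T2-weighted fast spin echo (FSE), fat saturated through the orbits and chiasm", and series 6 is its axial counterpart. Series 8 is "Axial Oblique T1-weighted Fat Suppressed gradient echo post contrast, optic nerves and chiasm", and series 9 is the coronal counterpart, also T1-weighted, fat-suppressed, gradient echo and post contrast.

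Section 10.2 (Methodology to Determine Tumor Measurement) gives a second nine-item list, this time with scanner settings. Before contrast it has "5) Coronal 2D, fat saturated TSE through the orbits and chiasm (TR ~3,500, Te ~80") and "6) Axial 2d, fat saturated TSE through the orbits and chiasm (TR ~3,500, Te ~80"). After contrast it has a whole-brain SPGR as series 7, then "8) Coronal 2d, fat saturated TSE through the orbits and chiasm (TR ~3,500, Te ~80") and "9) Axial 2d, fat saturated TSE through the orbits and chiasm (TR ~3,500, Te ~80"). It adds "Series 5 and 8 should have the same slice locations", and the same for series 6 and 9.

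Secondary objective 1.2.3 is "To compare response categories and EFS across the 3 MR sequences (T2-weighted, FLAIR, T1-weighted post-contrast"). Section 9.10 analyses it by percent agreement over follow-up scans, with bootstrap intervals, and by a proportional hazards model for dependent survival data.

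**The concern.** The two lists specify different images for the same purpose, and neither section says which governs. Section 10.2 is the only one with numeric settings, so it is a natural source for programming the scanner. Taken literally, it produces a second set of T2-type images of the orbits and chiasm after contrast, and no dedicated T1-weighted set.

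T1-weighted post-contrast is one of the three readings that objective 1.2.3 compares. For optic nerve and chiasm tumours, the series that 2.8 requires for that reading would be absent, or would be present at some time points and absent at others if the lists were used interchangeably. The retrospective central review in 10.9 could not recover images that were never acquired.

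**Working it through.** The plan attaches no figure to this point, so the check is a line-by-line comparison of the two lists.

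| Series | Section 2.8 | Section 10.2 |
|---|---|---|
| 5 (pre-contrast) | Coronal, T2-weighted FSE, fat saturated | Coronal, 2D TSE, fat saturated, TR ~3,500, TE ~80 |
| 6 (pre-contrast) | Axial, T2-weighted FSE, fat saturated | Axial, 2D TSE, fat saturated, TR ~3,500, TE ~80 |
| 7 (post-contrast) | Axial volumetric T1-weighted gradient echo, whole brain | Axial SPGR, whole brain |
| 8 (post-contrast) | Axial oblique, T1-weighted gradient echo, fat suppressed | Coronal, 2D TSE, fat saturated, TR ~3,500, TE ~80 |
| 9 (post-contrast) | Coronal, T1-weighted gradient echo, fat suppressed | Axial, 2D TSE, fat saturated, TR ~3,500, TE ~80 |

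1. **Within 10.2.** Series 8 equals series 5, and series 9 equals series 6, in plane, sequence type, fat saturation, TR and TE. Only the timing relative to contrast differs.

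2. **Weighting of those settings.** Section 10.2 does not itself label series 5 and 6. Two places in the protocol supply the label. Section 2.8 calls the same two series T2-weighted, and series 3 of 10.2, marked T2-weighted, has TR ~4500 and TE ~75, close to the TE of ~80 here. So 10.2 gives series 8 and 9 T2-type settings.

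3. **Between the sections.** Series 8 and 9 conflict on weighting (T1 against T2-type) and on sequence type (gradient echo against TSE). The plane order is also reversed: 2.8 has axial oblique then coronal, and 10.2 has coronal then axial.

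4. **What remains under 10.2.** Series 7 has the same position, plane and coverage as the series that 2.8 calls T1-weighted. It is therefore the one source of T1 post-contrast information for the orbits and chiasm. Section 10.2 neither targets it to that region nor says whether it is fat-suppressed.

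5. **Extent.**
   - Series: 2 of 9.
   - Segments in 10.3: right optic nerve, left optic nerve and chiasm/hypothalamus, which is 3 of up to 5.
   - Time points in the 7.1 table: baseline, then before cycles 4, 7, 10, 13, 16, 19, 22 and 25, which is 8 scheduled on-treatment scans, plus one when the patient leaves therapy.
   - Patients: the plan gives no expected share with optic nerve or chiasm/hypothalamic tumour, so the number could lie anywhere from 0 to 17 evaluable patients. The ceiling on scheduled on-treatment scans is 17 × 8 = 136, reached only if all 17 had such tumours and completed treatment.

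6. **Route to the endpoints.** Section 10.4 does not let a change in enhancement on post-contrast T1 decide response or progression alone. It requires a measurable change on FLAIR/T2 or on pre-contrast T1. Those series are in both lists, so the primary call does not depend on series 8 and 9. Objective 1.2.3 and the comparison in 9.10 do use a T1 post-contrast reading.

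**The case against.** The strongest reply is that this is a copied parameter line with little consequence. Section 2.8 calls its list a minimum, 10.4 takes for granted that post-contrast T1 images exist, and objective 1.2.3 names that sequence, so the intent is clear. Care is at one centre (9.12), scans are interpreted with the neuroradiologist (7.1), the same scanner is preferred (9.10), and 10.4 asks for an unchanged plane and sequence at follow-up. Much of this stands. A copying error is the likeliest explanation, and nothing suggests that one patient's scans would actually alternate between lists. But no text says that 2.8 prevails, and following 10.2 as printed omits two series that 2.8 requires.

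A reader might also infer more than the documents support:

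- **That T1 post-contrast imaging is lost altogether.** It is not, because series 7 remains. Neither 1.2.3 nor 9.10 demands the orbit series or fat suppression by name.
- **That agreement between T1 and T2 would be inflated by imaging the same contrast twice.** This needs a reader to score T2-type images as T1, which the plan nowhere provides for. Readings taken from series 7 would not have this problem.
- **That the slice-matching rule cannot be met.** Within 10.2 it works: 5 and 8 are both coronal, 6 and 9 both axial. It fails only if applied to the numbering of 2.8.
- **That series 7 is under-specified and lacks fat suppression.** Its TR/TE is blank in the text available here, which may be a gap in text extraction. On fat suppression 10.2 is silent.

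**Conclusion.** The contradiction is real and literal. As written, 10.2 replaces the two dedicated T1-weighted fat-suppressed post-contrast series with T2-type ones, and the protocol does not resolve the conflict. The consequence is confined to secondary objective 1.2.3 and the 9.10 comparison in patients with optic nerve or chiasm/hypothalamic tumour, where T1 post-contrast information would rest on the whole-brain series alone, and to comparability of scans if both lists are in use. The primary response rate is largely protected.

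This rests on two assumptions: that some scanner set-up follows 10.2 as printed, and that 2.8 states the intended weighting, as 1.2.3 and 10.4 suggest. The effect on the agreement estimates cannot be quantified, because the plan gives neither the tumour-site mix nor the series each reading is taken from. The point should be corrected, but it does not threaten the trial's main conclusion.

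**What to change.** - In 10.2, replace series 8 and 9 with the T1-weighted fat-suppressed post-contrast series of 2.8. Section 2.8 states no TR or TE, so the study's neuroradiologist must supply the T1 settings.
- Use one numbering and one plane order in both sections, so that the pairs 5/8 and 6/9 stay in the same plane and the slice-location rule holds under either list.
- State that T1 post-contrast readings for objective 1.2.3 and 9.10 use only T1-weighted series.
- While editing, check whether series 7 has its TR/TE in the source file.
- If scans have already been acquired, check which settings were used and record this for the 1.2.3 analysis.

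The cost is protocol wording and a check of the scanner programme. The number of series stays at nine.

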10.3 Tumor measurement

Given the complexity of JPA/ OPG, the tumor size/response will be assessed in different segments:

1. Optic nerve (right, left)

2. Chiasm /hypothalamus
3. Brain parenchyma / retrochiasmatic visual pathways (optic tracts, optic radiations, internal capsule, posterior fossa) (right/left).

Therefore, up to 5 measurements may be necessary.

1. Longest diameter of target lesion(s) measured from the axial plane or the plane in which the aspect of the tumor is best seen or measured, provided the same plane is used in follow ups.
2. The longest measurement of the tumor (or width, W) should be determined.
3. The perpendicular measurements (transverse (T) measurement-perpendicular to the width in the selected plane. The length (L) – tumor extent in the plane perpendicular to the selected plane will not be used for measurement purpose.
4. The lower limit of the target lesion(s) should be at least twice the thickness of the slices showing the tumor to decrease the partial volume effect (e.g. 8 mm lesion for a 4 mm slice).
5. An automated tool (OncoTreat) will be employed to evaluate how the values obtained with this tool compare with the manually derived values. The manually derived values will be the measurements used for the study.

10.4 Determination of tumor progression/response.

Progressive disease

Any patient with clinical or radiographic evidence of progressive disease following any treatment cycle will no longer receive pegylated interferon alfa-2b (see Section 5.1). Radiographic progression is defined as appearance of new tumors or an increase in any previously measurable lesion by $\geq 25\%$ in the product of the two longest perpendicular diameters or by 40% in the product of the three diameters. The preferred method for tumor measurement is to use the 3 diameters when available.

If possible, tumor progression should be documented by the appropriate radiological study. For patients who develop worsening neurological symptoms, attempts should be made to distinguish progressive disease from other causes prior to removing the patient from the study

Determination of tumor response or progression will be based on the pre-study baseline scan performed closest to time of study entry. Progressive disease will be defined based on the comparison of the baseline scan to the scan demonstrating best response.

1. The amount of tumor enhancement is quite variable in LGGs from one scan to the next. Therefore, tumor response/progression will not solely be determined by change in the amount of enhancing disease on post contrast T1 images. Measurable change in size/extent must be present on FLAIR/T2 images, or on pre-contrast T1 images.

2. Development of new disease or progression in any established lesions is considered progressive disease, regardless of response in other lesions – e.g. when multiple lesions show opposite responses, the progressive disease takes precedence.

Note:

- CT scans should not be used to determine response. For MRI imaging, the longest diameter can be measured from the axial plane or the plane in which the tumor is best seen or measured, provided the same plane and MR sequence is used in follow ups.
- The cystic components of a tumor are considered in separate tumor measurements. See options below.

Options:

- If the cyst/necrosis is eccentric, the W, T and L of the solid portion should be measured, the cyst/necrosis excluded from measurement.
- If the cyst/necrosis is central but represents a small portion of the tumor (<25%), disregard and measure the whole lesion.
- If the cyst/necrosis is central but represents a large portion of the tumor, identify a solid aspect of the mass that can be reproducibly measured.
- Leptomeningeal tumor spread is usually not a target lesion, and usually cannot be measured accurately. Presence and location of leptomeningeal tumor spread should be noted, change in extent/thickness assessed on follow up studies.
- For patients with large cystic components (>25%): One cystic component should be identified in the baseline scan. It should be measured separately from the solid component. It should be measured in 3 dimensions in the best sequence likely the T2 sequences. (L x T x W).

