10.5 Overall Response Assessment

The overall response assessment takes into account response in both target and non-target lesion, and the appearance of new lesions, where applicable, according to the criteria described in the table below. The overall response assessment is shown in the last column, and depends on the assessments of target, non-target, and new lesions in the preceding columns.

Target Lesions	Non-target Lesions	New Lesions	Overall Response
CR	CR	NO	CR
CR	IR/SD	NO	PR
PR	NON-PD	NO	PR
CR OR PR	NON-PD	NO	PR
SD	NON-PD	NO	SD

PD	ANY	YES OR NO	PD
ANY	PD	YES OR NO	PD
ANY	ANY	YES	PD

Abbreviations: CR: complete response; IR: incomplete response, PD: progressive disease; PR: partial response; SD; stable disease.

The section that follows will discuss the selection and evaluation of each of these types of lesions.

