10.6 Selection of Target and Non-Target Lesions

1. For most CNS tumors, only one lesion/mass is present and therefore is considered a “target” for measurement/follow up to assess for tumor progression/response.
2. If multiple measurable lesions are present, up to 5 should be selected as “target” lesions. Target lesions should be selected on the basis of size and suitability for accurate repeated measurements. All other lesions will be followed as non-target lesions (including CSF positive for tumor cells).
3. The lower size limit of the target lesion(s) should be at least twice the thickness of the slices showing the tumor to decrease the partial volume effect (e.g. 8 mm lesion for a 4 mm slice).
4. Any change in size of non-target lesions should be noted, though does not need to be measured.

10.7 Response Criteria for Target Lesions:

Response criteria are assessed in 3 dimensions – the product of L x W x T. An elliptical model volume ($=0.5L \times W \times T$) is used.

To assess response/progression, the ratio is calculated:

$$\mathbf{L \times W \times T \text{ (current scan) / L \times W \times T \text{ (reference scan)}}$$

Development of new disease or progression in any established lesions is considered progressive disease, regardless of response in other lesions – e.g. when multiple lesions show opposite responses, the progressive disease takes precedence. Response Criteria for 3-dimensional target lesions:

Complete Response (CR): Disappearance of all target lesions.

Partial response (PR): $\geq 65\%$ decrease in the sum of the products of the three perpendicular diameters of all target lesions (up to 5), taking as reference the initial baseline measurements.

Stable Disease (SD): Neither sufficient decrease in the sum of the products of the three perpendicular diameters of all target lesions to qualify for PR (taking as reference the initial baseline measurements), nor sufficient increase in a single target lesion to qualify for PD, (taking as reference the smallest disease measurement since the treatment started).

Progressive Disease (PD): 40% or more increase in the product of perpendicular diameters of ANY target lesion, taking as reference the smallest product observed since the start of treatment, or the appearance of one or more new lesions.

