In the rare circumstance that the length of a lesion cannot be determined, then comparison of 2 dimensional measurements, T x W (product of the longest diameter and its longest perpendicular diameter) can be used.

Response Criteria for 2-dimensional target lesions:

Complete Response (CR): Disappearance of all target lesions.

Partial response (PR): ≥50% decrease in the sum of the products of the two perpendicular diameters of all target lesions (up to 5), taking as reference the initial baseline measurements.

Stable Disease (SD): Neither sufficient decrease in the sum of the products of the two perpendicular diameters of all target lesions to qualify for PR (taking as reference the initial baseline measurements), nor sufficient increase in a single target lesion to qualify for PD, (taking as reference the smallest disease measurement since the treatment started).

Progressive Disease (PD): 25% or more increase in the product of perpendicular diameters of ANY target lesion, taking as reference the smallest product observed since the start of treatment, or the appearance of one or more new lesions.

Local progression is defined as progression of known residual tumor or the appearance of tumor at known prior sites of disease that were at some point without evidence of disease. Distant progression is defined as the appearance of tumor at sites other than known prior sites of disease. Distant progression most often occurs in the subarachnoid space and may occur at any point within the neuraxis. Although rare, extra- CNS metastasis represents distant failure. Combined local and distant progression is defined when evaluation of the entire neuraxis reveals local and distant progression.

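### Section 10.4 ties progression to the pre-study baseline scan and 10.7 to the smallest product on treatment; the removal rule cites 10.4 and the EFS definition cites neither, so a lesion that shrank has two possible progression thresholds

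*Combined protocol and SAP*

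**What the plan says.** Three statements bear on the reference scan for progression.

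- **10.4, baseline sentence:** "Determination of tumor response or progression will be based on the pre-study baseline scan performed closest to time of study entry". It covers both response and progression.
- **10.4, next sentence:** "Progressive disease will be defined based on the comparison of the baseline scan to the scan demonstrating best response". Section 2.8 repeats it almost word for word: "Progressive disease will be defined on the basis of a comparison of the baseline scan to the scan demonstrating best response". Neither version mentions the current scan.
- **10.7:** progressive disease is a 40% increase (three diameters) in any target lesion, "taking as reference the smallest product observed since the start of treatment". The two-dimensional version is a "25% or more increase in the product of perpendicular diameters of ANY target lesion", with the same reference. Both stable-disease definitions agree, "taking as reference the smallest disease measurement since the treatment started". Partial response is measured from baseline.

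The sentence in 10.4 that gives the 25% and 40% figures names no reference scan, and it applies to any previously measurable lesion rather than any target lesion.

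The cross-references divide. After the overall-response table, 10.5 says "The section that follows will discuss the selection and evaluation of each of these types of lesions", which leads to 10.6 to 10.8. Sections 8.1 (removal from therapy) and 5.0 (dose reductions) cite 10.4 for progressive disease. The EFS definition in 9.3.1.2 cites no section. Section 9.4 assigns progression to institutional review and 10.9 adds retrospective central review; neither names a reference scan.

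**The concern.** The percentages agree and only the reference differs, so the conflict is invisible until a target lesion shrinks and then regrows. At that point a reader following 8.1 to 10.4 and a reader using 10.7 can classify the same scan differently. Institutional and central reviewers could also do so, because neither is told which reference to use.

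Two things depend on the answer. One is the EFS date, a secondary endpoint that also feeds the comparison across MR sequences in 9.10; progression is a censoring event in the toxicity analysis of 9.8 as well. The other is treatment: 10.4 says "Any patient with clinical or radiographic evidence of progressive disease following any treatment cycle will no longer receive pegylated interferon alfa-2b", although 4.4 permits a further cycle if the investigator judges that the patient is benefiting.

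**Working it through.** The plan states no worked figure on this point to reproduce. The check puts the two references on one scale.

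**Inputs.** Increase required, g = 0.40 (three diameters) or 0.25 (two), the same in 10.4 and 10.7. Smallest size on treatment as a fraction of baseline, s. The value s = 0.35 is a lesion that just meets the three-dimensional partial response in 10.7 (65% decrease), and s = 0.50 just meets the two-dimensional one (50% decrease). The value s = 0.80 illustrates lesser shrinkage. A single target lesion is assumed. Both dimensions are shown because 10.4 and 10.7 prefer three diameters while 10.3 says length will not be used.

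**Formulas.** Threshold as a fraction of baseline: smallest-size rule (10.7) = s × (1 + g); baseline sentence (10.4) = 1 + g. Regrowth from the smallest size needed under the baseline sentence = (1 + g)/s − 1.

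| Dimensions | s | 10.7 threshold | 10.4 baseline threshold | Regrowth needed, 10.7 v baseline |
|---|---|---|---|---|
| 3 | 0.80 | 0.80 × 1.40 = 112% | 140% | 40% v 75% |
| 3 | 0.50 | 0.50 × 1.40 = 70% | 140% | 40% v 180% |
| 3 | 0.35 | 0.35 × 1.40 = 49% | 140% | 40% v 300% |
| 2 | 0.80 | 0.80 × 1.25 = 100% | 125% | 25% v 56% |
| 2 | 0.50 | 0.50 × 1.25 = 62.5% | 125% | 25% v 150% |

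The thresholds differ by the factor 1/s: 1.25, 2.00 and 2.86 for s = 0.80, 0.50 and 0.35. With no shrinkage they coincide at 140% and 125%, provided the baseline scan may count as the smallest.

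**Direction.** For s below 1 the baseline threshold is always the higher, so it is met at the same scan or a later one. It is the same scan if the lesion passes both thresholds between two 12-weekly scans, and the EFS date is also unchanged if new-lesion, non-target or clinical progression comes first. The documents give no regrowth rate, so no length of delay follows.

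**Response count.** Section 10.7 measures partial response from baseline under either reading, and 9.4 keeps a recorded response after later progression. One route remains: a patient with less than partial-response shrinkage who is removed earlier under the smallest-size rule could lose a later response.

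**The case against.** The strongest reply is that the documents already lean to one answer. Section 10.7 alone gives percentage, lesion and reference scan together, in both dimensions and with matching stable-disease definitions, and 10.5 leads to it. The second sentence of 10.4 concerns progression specifically and mentions the best-response scan, so it may be a garbled smallest-size rule; on that reading the difference is zero. The pointers to 10.4 are also weak evidence of intent, since cross-references elsewhere are wrong: 10.4 cites 5.1, a toxicity section, for stopping at progression, and 4.1 places the diary in Appendix 5 when it is Appendix 4.

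Much of this stands. A reader might infer that the protocol adopts a baseline rule for progression, or has no usable rule; 10.5 and 10.7 do not support either. But the second sentence names no current scan and so yields no threshold as written, it directly follows a sentence that names baseline for progression, and no text says that 10.7 prevails for removal or EFS.

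It is also fair that the consequence is bounded. EFS is secondary in a single-arm trial planned for 17 evaluable patients, and the sample size in 9.2 does not rest on it.

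**Conclusion.** The conflict is real and should be corrected before progression dates are analysed. Its size is the threshold gap: for a three-dimensional lesion that just met partial response, progression at 140% of baseline instead of 49%; for one that shrank to 80%, 140% instead of 112%. This rests on someone applying 10.4's baseline sentence, which its wording permits and 8.1 invites, and only to target lesions that shrank below baseline.

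Two stronger conclusions are tempting and unsupported. The first is that EFS would be lengthened by a given number of weeks: that needs a regrowth rate the documents do not contain, and the delay can be zero. The second is that the primary result or the two-stage decision is compromised. Section 9.5 does mention disease progressions among the bases for stopping, but its decision table uses responders only. The response count is largely unaffected, apart from the possible loss of a later response after earlier removal.

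**What to change.** Amend the text to follow 10.7:

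- **10.4, percentage sentence:** make it read *an increase in any target lesion on the current scan of 25% or more (2D) or 40% or more (3D) over its smallest product on study, including the pre-study baseline scan (see 10.7)*. This supplies the missing reference and aligns the lesion scope. Keep new tumors, clinical progression and non-target progression (10.8) as progressive disease.
- **10.4, baseline sentence:** remove the mention of progression, so that baseline is the reference for response only.
- **10.4 and 2.8:** delete the sentence comparing the baseline scan with the best-response scan.
- **8.1 and 9.3.1.2:** cite the corrected 10.4 together with 10.7 and 10.8.

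If the sponsor wants to keep treating a patient whose regrowing tumor is still below baseline, state that in 8.1 as a separate removal rule consistent with 4.4, and still date EFS by the smallest-size rule.

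The cost is one written amendment with IRB review (12.1), with no new scans or patients. The downside is that EFS may look shorter than under a baseline reference, and some patients may come off drug earlier unless a separate removal rule is written.
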